Continuous Glucose Monitoring (CGM) systems to ensure unbiased comparisons across the study groups. Simple randomization using computer-generated random numbers will be implemented to allocate patients randomly. This method will help distribute confounding variables evenly between groups, thereby minimizing selection bias. Block randomization may also be utilized to maintain balance in the number of participants among the groups throughout the study. Allocation concealment will be maintained until the intervention assignment to prevent any potential influence on patient enrollment.

Statistical method

Definition of Analysis Sets

The following data sets will be analyzed:

- Full analysis set (FAS):
The set of subjects is as close as possible to the ideal implied by the intention-to-treat principle. All subjects with at least one efficacy follow-up will be included. It is derived from the set of all eligible subjects by minimal and justified elimination of subjects. When handling of missing values of primary outcomes, the last observation carried forward (LOCF) method will be applied.
- Per-protocol analysis set (PPS):
The per protocol analysis set will consist of all patients in the full analysis set plus the following criteria: completion the treatment process, without any major protocol violations, good compliance (80%~120% medical device and capillary finger sticks compliance) and without missing value in primary outcomes. Patients with at least one major protocol violation (e.g missing the 8 weeks efficacy follow up) will be excluded from the per-protocol analysis.
- Safety Set (SS):
The safety set will consist of all subjects followed at least one period with one CGM system.

Endpoints:

Primary: number of episodes of pre-set hypoglycemia (hypoglycemia <70 mg/dL and severe hypoglycemia < 54 mg/dL), time above, under or in pre-set target range, glycemic variations during the different periods of use of CGM tools based on different alarms;

Secondary objectives

Secondary: accuracy and MARD (comparator finger capillary sticks) during the use of two different CGM; perspectives and preferences in monitoring and specific use of different alarms with Dexcom One Plus or with Dexcom G7; correlation of primary endpoint with the quality of sleep, quality of life and/or neurocognitive outcomes i.e. attention, assessed by specific questionnaires; perspectives and preferences in monitoring and specific use of different CGM with Usual Care monitoring.

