- Compliance of study: study compliance to the CGM two medical devices and capillary finger sticks of all groups will be described and compared. A list of subjects with poor compliance (80% below or 120% above compliance) will be generated.

Observation parameters list (CRF)

Patients at screening, baseline, after 30 days of **unblinded monitoring** with Dexcom G7 and 30 days of **unblinded monitoring** with Dexcom One Plus (Fig. 2). The start of the single CGM tool will be randomized (i.e. 50% of patients will random start with G7 and then switch to Dexcom One Plus, and *viceversa*).

- 1) SCREENING _ General data collection: age, gender, height, body weight, minority, career, income, degree of education, family history, smoking habit, primary diseases or accompanied diseases.
- 2) SCREENING _ Previous glucose monitoring (referring to the last 8 weeks): number of capillary fingers sticks per day, use (or not) of CGM and type of CGM device
- 3) SCREENING _ Major comorbidities
- 4) SCREENING _ Document intake of medications
- 5) SCREENING _ Adverse events and the rate of hospitalization during the last year
- 6) BASELINE _ Quality of Life (SF-12 rating scale)
- 7) BASELINE _ Quality of Sleep (Pittsburgh sleep quality index (PSQI))
- 8) FOLLOW UP _ Capillary finger sticks glucose values (3 per day) by diary record

- 9) FOLLOW UP_ CGM values: time above, under or in the pre-set target, number of episodes of pre-set hypoglycemia
- 10) FOLLOW UP_ CGM tolerance, perspectives and expectations (Specific questionnaires)
- 11) FOLLOW UP_ CGM Quality of Sleep (Pittsburgh sleep quality index (PSQI), quality of life (SF12))
- 12) FOLLOW-UP_ Education on the use of CGM device (sensor, receiver or other tools)

Flowchart indicating which parameter is measured when:

Observation Parameters	Screening	Enrollment/Baseline	Follow up - After 30 days	Final Visit study - After 30 days
Informed consent	x			
Demographic (Age, Gender, Career, Degree of Education, Income)	x			
Height	x			
Body Weight	x	x	x	x
Family History	x			
Smoking Habit	x			
Physical exam	x			
Vital signs	x			
Primary Diseases or Accompanied Diseases	x			
Major IMD Comorbidities	x			
Glucometer values		x	x	x
Use of CGM	x			
Documented Intake of Medications	x			
Rate of Hospitalization During the Last Year	x			
Type of CGM Device	x	x	x	x
Capillary finger sticks glucose values (3 per day)		x	x	x
CGM values (time in pre-set hypoglycemia, number of pre-set hypoglycemia, MARD)		x	x	x

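### The 120% upper compliance limit can remove patients from the per-protocol set for taking extra finger sticks, which do no harm and may be related to hypoglycemia and to the device

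*Combined protocol and SAP*

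**What the plan says.** In the combined protocol and SAP, under Definition of Analysis Sets, the PPS is restricted to full-analysis-set patients who complete treatment without major violations and have "good compliance (80%~120% medical device and capillary finger sticks compliance) and without missing value in primary outcomes". Under Statistical Analysis, item (3) Compliance, the same limits return: "A list of subjects with poor compliance (80% below or 120% above compliance) will be generated".

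The planned number of sticks is in the Observation parameters list: "FOLLOW UP _ Capillary finger sticks glucose values (3 per day) by diary record". Under Endpoints, finger sticks are the comparator for sensor accuracy and MARD, which is secondary. The first primary endpoint is "number of episodes of pre-set hypoglycemia (hypoglycemia <70 mg/dL and severe hypoglycemia < 54 mg/dL"), and the parameters list takes these counts from the CGM data.

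The PPS text adds: "Patients with at least one major protocol violation (e.g missing the 8 weeks efficacy follow up) will be excluded from the per-protocol analysis". The flowchart has screening, baseline, a follow-up after 30 days, and "Final Visit study - After 30 days".

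The full analysis set (FAS) has no compliance filter. The plan does not say whether the FAS or the PPS is primary. It does not say how compliance is calculated: all sticks or only scheduled ones, per period or overall, and for the device, wear time or sensors used.

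**The concern.** An upper limit suits a treatment that can be overused. Here the finger stick is a reference measurement, and additional readings cost the accuracy analysis nothing. The plan gives no reason for treating them as poor compliance.

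The number of extra sticks arises after randomization. Patients see their glucose values and alarms, and the devices differ in alarm type (threshold for Dexcom One Plus, predictive for Dexcom G7). A patient who checks a low reading or an alarm with a finger stick adds to the count, so the count may be related both to the primary outcome and to the device. Long-standing habit could also matter: a patient used to four sticks a day who simply continues reaches 120 / 90 = 133% of plan.

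At stake is a PPS that describes a cohort with less hypoglycemia than the one enrolled, and that is smaller than it needs to be in a trial of 11.

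**Working it through.** The plan derives no figure on this point; its sample size of 11 is justified by rarity alone. The check starts from the planned stick count.

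**Limits in sticks** (3 per day; 80% and 120% from the PPS definition)

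| Basis | Planned | 80% | 120% | Extras allowed at full adherence |
|---|---|---|---|---|
| 30 days | 3 × 30 = 90 | 72 | 108 | 18 |
| 60 days | 3 × 60 = 180 | 144 | 216 | 36 |

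In both cases this is 18 / 30 = 0.6 extra sticks per day, or 0.6 × 7 = 4.2 per week. At 90% adherence (81 of 90 done) the margin is 108 − 81 = 27 extras, or 27 / 30 × 7 = 6.3 per week. One excluded patient is 1 / 11 = 9.1% of the sample.

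**Device.** Wear time cannot exceed 100%, so on that measure the upper limit excludes nobody. A count of sensors used could exceed 100%; the plan does not say which is meant.

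**Does the limit select on hypoglycemia?** The documents give neither an episode rate nor the share c of episodes that prompt one extra recorded stick. Both are assumed below, and all recorded sticks are taken to count.

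One patient, one 30-day period: P(X > allowed extras), X ~ Poisson(rate × 30/7 × c).

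| Episodes/week | c | P(excluded), all 90 done | P(excluded), 81 done |
|---|---|---|---|
| 2 | 1 | 0.001 | 0.000 |
| 4 | 0.5 | 0.001 | 0.000 |
| 4 | 1 | 0.358 | 0.010 |
| 7 | 0.25 | 0.000 | 0.000 |
| 7 | 0.5 | 0.181 | 0.002 |
| 7 | 1 | 0.987 | 0.667 |

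Eleven patients, 60 days, 95% adherence, patient rates spread exponentially, 4,000 simulated trials per row:

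| Mean episodes/week assumed | c | FAS mean | PPS mean | Mean number excluded of 11 |
|---|---|---|---|---|
| 2 | 0.25 | 1.99 | 1.99 | 0.0 |
| 2 | 1 | 2.02 | 1.58 | 0.84 |
| 4 | 0 | 4.01 | 4.01 | 0.0 |
| 4 | 0.5 | 4.02 | 3.16 | 0.84 |
| 4 | 1 | 4.04 | 2.06 | 2.98 |
| 7 | 0.5 | 7.03 | 4.02 | 2.44 |

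At a mean of 4 per week, the patient with the most episodes is excluded in 57% of simulated trials at c = 0.5 and in 97% at c = 1. The effect therefore runs from nothing to a halving of the PPS mean.

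**Visit label.** Two 30-day periods run consecutively end on day 60, or 60 / 7 = 8.6 weeks. Eight weeks is day 56, which is day 26 of the second period and 4 days before the final visit. The only other use of eight weeks is the screening look-back, "Previous glucose monitoring (referring to the last 8 weeks"). The time-design figure is not shown in the text available, so this was checked against the text and the flowchart only.

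**The case against.** The title-level inference a reader might draw is that the rule removes the patients with the most hypoglycemia. The documents do not support that as fact. They contain no rule for confirmatory sticks and no statement that extra sticks follow low readings or alarms. The Study Background says CGM spares patients repeated capillary checks, so alarms might replace sticks. With two episodes a week, the chance of a fully adherent patient passing 108 is 0.1% even if every episode prompts a stick. This objection stands: only a possible preferential removal can be claimed.

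Compliance is also undefined. If it means scheduled sticks done over scheduled sticks, it cannot exceed 100% and the upper limit never acts. The flowchart lists meter values and the three-a-day sticks in separate rows, which is compatible with that reading. This stands too, but it does not defend the limit: on that reading the limit is empty, and on the other it excludes harmless behaviour.

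A reader might also infer that the device comparison is biased. The FAS keeps these patients, and each patient uses both devices, so exclusion removes both periods together. The contrast is distorted only if the device effect differs in those excluded. That could happen on an absolute scale if the effect is proportional to the level of hypoglycemia, but the documents do not show it.

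Finally, it is tempting to say that the PPS depends on a visit that does not exist. The 8-week follow-up is one example of a major violation, probably a loose name for the final visit. The PPS separately requires completion and no missing primary outcome, so the example would rarely change membership.

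**Conclusion.** The concern holds in a limited form. A rule stated twice can exclude a patient from the PPS for taking more than 108 sticks against 90 planned (216 against 180 over 60 days). This rests on all recorded sticks counting and, for the 18-stick margin, on full adherence to the schedule. The exclusion is post-randomization, has no stated purpose, and may track both outcome and alarm type.

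The consequence is confined to the PPS: a possible understatement of the level of hypoglycemia, and a loss of precision of 9.1% of the patients per exclusion. The size cannot be fixed from the documents; under the assumptions shown, the PPS mean ranges from equal to the FAS mean to about half of it. The limit matters more because the plan does not name either set as primary.

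The 8-week wording is a label mismatch of 4 days and no more than that.

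**What to change.** 1. Delete the 120% upper limit from the PPS definition and from the compliance listing; keep the 80% lower limit.
2. Define finger-stick compliance as scheduled sticks done divided by scheduled sticks, and device compliance as sensor wear time. State whether each is computed per period or over both periods. A requirement of 80% in every period would be a new condition that could exclude more patients, and this correction does not need it.
3. Report extra sticks by device as a descriptive result.
4. Reconcile the 8-week efficacy follow-up with the scheduled final visit at the end of the second 30-day period.

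The cost is a few sentences in the two sections, with no change to visits or data collection beyond marking which recorded sticks are scheduled. The edits should be made before the data are analysed, because with 11 patients an exclusion rule settled afterwards would be hard to defend.

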The current IMDs guidelines are cautious about the recommendations on the use of CGM and its clinical practice application in nutritional improvements or modifications (15–17). Rossi et al. have recently proposed indications for CGM monitoring and CGM outcome parameters in patients with hepatic GSDs (14). Peeks et al. also indicated outcome parameters for hepatic GSDs (13).

Worth et al. have recently analyzed the state of art of the evidence for the use of CGM in non-diabetic children with hypoglycemia (9). Some suggestions for qualified CGM use have been provided, but a focus on patients' perspectives on the use of different CGM systems is still lacking, especially on recent tools developed by new technologies.

Study Objectives

Primary objective

Assessment of Pre-set targeted time in hypoglycemia and number of episodes of pre-set hypoglycemia during the different periods of use of CGM tools based on different alarms.

Secondary objectives

Accuracy of the two different CGM systems (comparator SBGM by capillary finger stick).

Assessment of patients' perspectives and tolerance to the use of two subsequent different CGM systems and tools, in particular on different types of alarms: Dexcom One Plus (Dexcom) with threshold alarm and Dexcom G7 (Dexcom) with predictive alarm.

Assessment of quality of life and sleep quality.

Assessment and comparison of glycemic control, patients' perspective and tolerance of CGM with USUAL Care CGM.

Study Design

Study Type

Prospective interventional with medical devices CE

Study Site

Sample Size Estimation

11 IMDs at risk for hypoglycemia

The rare condition of disorders investigated needs to be considered for the sample size (e.g. GSD I has a frequency of approximately 1 in 100,000 and the estimated incidence of CHI ranges between 1:27,000 and 1:50,000 live births in outbred western population).

Randomization

Patients will be randomized to start with the use of Dexcom G7 o Dexcom One Plus after baseline.

Methods for randomization: Randomization will be employed to assign participants to different

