Statistical Analysis (example)

(1) General Principles

Quantitative variable will be described by the total number of cases, number of missing values, mean, and standard deviation, minimum, maximum and median. Categorical variables will be described by the number of cases and percentages.

All statistical tests will be performed using two-sided test, P value less than or equal to 0.05 will be considered to have examined the difference statistically significant (Unless otherwise noted). For comparison between two groups of the general condition, the suitable method shall be adopted to conduct analysis according to the type of indicators; for the comparison among groups of quantitative data, group t test (homogeneity of variance, normal distribution) or Wilcoxon rank-sum test will be adopted according to the data distribution (the Shapiro-Wilk test will be used beforehand to check whether the variables follow a normal distribution or not); for categorical data, the chi-square test or Fisher's exact test (if the chi-square test is not applicable) shall be adopted; for ordered data, Wilcoxon rank-sum test or Cochran-Mantel-Hansel test shall be adopted. Multiple regression analyses will also be considered, including linear regression for continuous dependent variables, Poisson regression and cumulative logit logistic regression for ordered response variables (or logistic regression for dichotomous variables, such as presence/absence). Moreover, ANOVA or mixed-effects models will be used to compare how the effect of interest varies over time within the same subject, repeated measures.

(2) Completion and Baseline Parameters

The summary of the study completion includes the count of completed cases of each study center, the list of dropout cases, the analysis set description, the comparison of dropout rates of the groups and the list of reasons for incompleteness. The summary of baseline parameters includes demographic characteristics (gender, age, height, vital signs etc.), history of illness and medications, and specific Questionnaires about CGM tolerance, perspectives and expectations. Comparisons among the two different CGM devices groups and gold standard by capillary finger stick will be conducted to evaluate MARD and reliability during the period of observation.

(3) Compliance

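### Six unranked primary outcomes against two in the primary objective, with a general 0.05 rule and no definition of success: roughly 11–24% chance of a false-positive primary result if any one counts

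*Combined protocol and SAP*

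**What the plan says.** Three parts of the combined protocol and SAP describe the primary outcomes, and they differ.

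- **Study Objectives, Primary objective:** "Assessment of Pre-set targeted time in hypoglycemia and number of episodes of pre-set hypoglycemia". This names two outcomes.
- **Endpoints, Primary:** "number of episodes of pre-set hypoglycemia (hypoglycemia <70 mg/dL and severe hypoglycemia < 54 mg/dL), time above, under or in pre-set target range", with glycemic variation added at the end of the same list. Counted singly, these are episodes below 70 mg/dL, episodes below 54 mg/dL, time above range, time under range, time in range, and glycemic variation. None is ranked, and the endpoint names no metric for glycemic variation.
- **Observation parameters list (CRF):** the flowchart lists time in hypoglycemia, number of episodes and MARD. Item 9 of the list above it also includes time above and in target. Neither mentions glycemic variation.

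A secondary endpoint is the "correlation of primary endpoint with the quality of sleep, quality of life and/or neurocognitive outcomes", which presupposes a single primary endpoint.

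On error control, Statistical Analysis, (1) General Principles says "All statistical tests will be performed using two-sided test" and "P value less than or equal to 0.05 will be considered to have examined the difference statistically significant (Unless otherwise noted"). Nothing is noted otherwise. No hierarchy, alpha split, co-primary rule or multiplicity adjustment appears anywhere. The sample size of 11 is justified by rarity alone, without effect size, standard deviation or power.

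**The concern.** A plan with six unranked primary outcomes and one general threshold does not say what a positive trial would look like. Any of the six could be put forward as the primary result once the data are seen. Results in opposite directions, such as less time low with more time high, have no rule for interpretation. Time above range also lies outside the hypoglycemia question in the primary objective. The correlation analysis cannot be carried out as written, because it is unclear which of the six is meant.

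**Working it through.** **Plan's own figure.** The documents state no familywise error rate and no power, so there is nothing to reproduce. The only error figure is 0.05 per test.

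**Inputs from the documents.** Six outcomes (Endpoints), two-sided 0.05 (General Principles), 11 patients (Sample Size Estimation), and each patient using both systems in randomized order (Observation parameters list).

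**Assumptions of this check.** No true difference on any outcome; any one significant result is claimed; a within-patient t test on 11 complete pairs; correlations as stated below.

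**Step 1. Independence reference.** 1 − 0.95^6 = 0.265, or 26.5%. This cannot occur here. Time above, in and below range sum to 100%, so their three within-patient differences sum to zero and cannot be mutually independent.

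**Step 2. Equal correlation among six tests.** The first column is numerical integration for z tests. The second is simulation of t tests with n = 11 (200,000 runs).

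| Correlation | z tests | t tests, n = 11 |
|---|---|---|
| 0.3 | 24.1% | 24.6% |
| 0.5 | 20.7% | 21.6% |
| 0.7 | 16.4% | 17.5% |
| 0.8 | 13.9% | 14.8% |
| 0.9 | 10.8% | 11.5% |

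This gives roughly 11–24%. The table is also only a guide, because one common positive correlation cannot hold exactly among three differences that sum to zero.

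**Step 3. Respecting the fixed sum.** Here the difference in time in range is set to minus the sum of the other two differences. The remaining correlations are assumed (n = 11, 200,000 runs). Time above range is uncorrelated with the hypoglycemia measures except in the last row, where that correlation is 0.2.

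| Among hypoglycemia measures | With glycemic variation | At least one false positive |
|---|---|---|
| 0.3 | 0.2 | 23.7% |
| 0.5 | 0.3 | 22.6% |
| 0.7 | 0.4 | 20.6% |
| 0.8 | 0.5 | 19.0% |
| 0.9 | 0.5 | 17.7% |
| 0.9 | 0.6 | 16.7% |

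Most settings give about 17–22%. The weakest correlations come a little above that, still within 24%.

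**Step 4. After restriction to the two outcomes of the objective.**
- Both at 0.05, unadjusted: 1 − 0.95² = 9.75% if independent; about 8.4% at correlation 0.7 (z tests). Shortening the list is therefore not enough without an error rule.
- Both at 0.025: at most 5% (1 − 0.975² = 4.9% if independent).
- Fixed sequence at 0.05: at most 5%.

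**Step 5. Cost in detectable difference.** Paired t test, 11 pairs, 80% power, in standard deviations of the paired difference: 0.94 at 0.05, 1.07 at 0.025, and 1.28 at 0.05/6. Against 0.94, these are increases of 1.07/0.94 = 1.14-fold and 1.28/0.94 = 1.36-fold.

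**The case against.** The best reply is that no confirmatory test of each outcome is actually specified. The statistical section is headed as an example and ties no test to any primary endpoint. The objective is phrased as an assessment, n = 11 rests on rarity, and the synopsis carries a second title describing an observational study. On that reading the trial is exploratory and familywise error is beside the point. Part of this stands: a 0.05 test of each outcome is the natural consequence of the general rule, not an explicit statement. But the main title speaks of efficacy, the order of devices is randomized, and a significance threshold is set for all tests. Nowhere is the study called exploratory. Leaving the tests open also adds analytic freedom.

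A second reply is that inflation needs an any-one-suffices rule, which the plan does not state. That is correct. If all six had to be significant, the error would not inflate. The plan states neither rule, so the rate is conditional.

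Three stronger readings are tempting and are not supported:
- **That the false-positive rate is 26.5%, or that 16% is its floor.** The first needs an independence that the fixed sum rules out. The second needs correlations near 0.7, whereas 0.8–0.9 gives about 11–15%.
- **That a single primary endpoint is the only sound choice because splitting alpha costs too much.** That follows only against a six-way Bonferroni split (1.28 SD). Two outcomes at 0.025 each need 1.07 SD against 0.94.
- **That the documents already point to time below 70 mg/dL as the primary.** The objective puts time first, but the endpoint list puts episodes first and attaches the 70 and 54 mg/dL cut-offs to episodes. The pre-set range for the time outcomes is not given a number.

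**Conclusion.** The point holds. The endpoint list, the objective and the singular reference to a primary endpoint do not agree, and no rule controls error or defines success across the six outcomes. This should be corrected before analysis.

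The size is conditional on the assumptions set out in the check and on a correlation structure the documents do not supply. The result is roughly 11–24%, and about 17–22% in most fixed-sum settings, against a nominal 5%. Even at a correlation of 0.9 the rate is about twice nominal. It counts false differences in either direction, so it is not the chance of a false benefit for one named system. Confidence is high in the gap itself and lower in any single figure within the range.

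**What to change.** Limit the primary endpoints to the two outcomes of the primary objective and state one error rule. Either option is sound:

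1. One primary endpoint tested at two-sided 0.05, and the other tested at 0.05 only if the first is significant. One possible order is percent of sensor time in pre-set hypoglycemia, then episode rate.
2. Both outcomes tested at 0.025.

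In either case the sponsor should state the threshold that defines the time endpoint and which threshold applies to the primary episode count. Move time above range, time in range, glycemic variation (with its metric named) and the other hypoglycemia threshold to secondary, reported as estimates with 95% confidence intervals and no confirmatory claim. Align the Primary objective, the Endpoints section and the Observation parameters list, including its flowchart, and say which endpoint the correlation analysis uses.

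The cost is wording only: no added patients, visits or data. The downside is that fewer outcomes can carry a claim of significance. Option 2 also raises the detectable difference from 0.94 to 1.07 SD under the paired t assumptions above.

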STUDY PROTOCOL (version 2 - 17/09/2024)

Study Title:

The efficacy of different Continuous Glucose Monitoring systems in a cohort of adult patients affected by Inherited Metabolic Disorders prone to Hypoglycemia

Study Type:

Interventional study with CE-marked medical device, single-center, spontaneous

Sponsor:

University Hospital of Padova

Principal Investigator:

[name], MD, PhD

[contact]

Email: [contact]

Coordinating Center:

Division of Metabolic Diseases

Director: [name]

University Hospital of Padova

[name]

Study Background	5
Study Objectives	6
Primary objective	6
Secondary objectives	6
Study Design	6
Study Type	6
Study Site	7
Sample Size Estimation	7
Randomization	7
Statistical method	7
Definition of Analysis Sets	7
Endpoints:	7
Statistical Analysis (example)	8
Observation parameters list (CRF)	8
Study Duration	10
Schematic Study Plan	10
Figure 2. Time design of the study (arrows correspond to a sensor change or a device/system switch)	11
Study Population	11
Inclusion Criteria	11
Exclusion Criteria	11
Study Evaluation	11
Study Quality Control	11
Requirements of Ethics	12
Management Principles	12
Resume	12
Record Storage in the Study Site	12
Protocol Revision	12
Termination of Study Protocol	12
References	13

Abbreviations (examples/alphabetical order)

Abbreviation	Definition
CGM:	continuous glucose monitoring;
CH:	congenital hyperinsulinisms;
FGM:	flash glucose monitoring;
GSD:	glycogen storage disorders;
GV:	glycemic variation;
IMD:	inherited metabolic disorders;
MARD:	mean absolute relative difference;
Rt-CGM:	real time continuous glucose monitoring;
SMBG:	self-monitoring blood glucose;
TAR:	time above range;
TIR:	time in range;
T1DM:	type 1 diabetes mellitus;

Trial Title	The use of Continuous Glucose Monitoring in Inherited Metabolic Disorders prone to Hypoglycemia: Patients' Perspectives and Reliability between Different Devices from an Observational Study
Principal Investigator	[name]
Study Objective/research question	Assessment of perspectives and glycemic reliability of different real time CGM devices in a cohort of adult IMDs patients prone to hypoglycemia
Study Design	Prospective interventional with medical devices CE

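### Alarm type is tied to the device that measures the primary outcome and no signed accuracy measure is specified, so a calibration difference, if one exists, could be read as an alarm effect

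*Combined protocol and SAP*

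**What the plan says.** - **Primary endpoint** (Endpoints): "number of episodes of pre-set hypoglycemia (hypoglycemia <70 mg/dL and severe hypoglycemia < 54 mg/dL), time above, under or in pre-set target range", plus glycemic variation, compared "during the different periods of use of CGM tools based on different alarms".
- **Source of the outcome** (Observation parameters list (CRF), item 9): "CGM values: time above, under or in the pre-set target, number of episodes of pre-set hypoglycemia". No common or blinded reference sensor is planned, so each period is measured by the device worn in it.
- **Devices** (Secondary objectives): "Dexcom One Plus (Dexcom) with threshold alarm and Dexcom G7 (Dexcom) with predictive alarm". Each patient uses both for 30 days, unblinded, in random order.
- **Accuracy**: a secondary objective, listed under Endpoints as "accuracy and MARD (comparator finger capillary sticks) during the use of two different CGM". Under Statistical Analysis, item (2), comparisons of the devices with the "gold standard by capillary finger stick will be conducted to evaluate MARD and reliability during the period of observation". The Abbreviations expand MARD as "mean absolute relative difference". *Accuracy* and *reliability* are not defined.
- **Reference data** (CRF item 8): three finger sticks a day, kept in a diary.

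No signed bias, calibration adjustment or bias sensitivity analysis of the primary outcome is described.

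**The concern.** Each device is both the intervention and the measuring instrument. Time below a fixed cut-off is sensitive to small shifts in the readings, because much of the distribution can lie just above the cut-off. Randomizing the order does not help, since a device's bias goes with it in either sequence.

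The plan treats relative accuracy as an open question but does not carry the answer into the primary comparison. The one metric it names cannot show direction: a device reading high and one reading low by the same relative amount can have the same MARD. The contrast is worded in terms of alarms, so a difference that came from the instruments could be credited to the alarm type.

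**Working it through.** The plan gives no glucose distribution, device bias or error SD, and supports its sample size of 11 by rarity alone. There is thus no planned figure to reproduce. The distributions, shifts, error SDs and ICCs below are assumptions.

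**1. Effect of a shift on time below 70.** If glucose is normal with mean m and SD s, and the device reads b too high (b negative if low), measured time below 70 is Φ((70 − m − b)/s).

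| m / s (mg/dL) | b = 0 | b = −3 | b = −5 |
|---|---|---|---|
| 100 / 20 | Φ(−1.50) = 6.68% | Φ(−1.35) = 8.85% (×1.32) | Φ(−1.25) = 10.56% (×1.58) |
| 90 / 15 | Φ(−1.33) = 9.12% | Φ(−1.13) = 12.85% (×1.41) | Φ(−1.00) = 15.87% (×1.74) |

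Across five combinations with mean 95 to 110 and CV 15% to 25%, normal and lognormal, the multiplier is 1.22 to 1.87 for 3 mg/dL low and 1.39 to 2.70 for 5 mg/dL low. Multipliers for time below 54 are larger, but from small baselines (2.09% at most).

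**2. What MARD can show.** For normal relative error with mean b and SD s, MARD = s·√(2/π)·exp(−b²/2s²) + b·[1 − 2Φ(−b/s)]. This is the same for +b and −b. With s = 10%:
- b = 0: 7.98%
- b = +3% or −3%: 8.34% for both
- b = +5% or −5%: 8.96% for both

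Two devices with equal MARDs of 8.34% could thus differ by 6% of 70 = 4.2 mg/dL at the cut-off; at 8.96%, by 10% of 70 = 7 mg/dL.

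**3. Chance of a significant result with no alarm effect.** Simulated crossover: 11 patients, patient means around 100 mg/dL with SD 10, glucose SD 20, 20,000 trials per cell, paired t test on time below 70, two-sided 0.05.

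| SD of a patient's period mean (mg/dL) | No shift | 3 mg/dL shift | 5 mg/dL shift |
|---|---|---|---|
| 2 | 4% | 77% | 99% |
| 3 | 4% | 44% | 85% |
| 5 | 4% | 19% | 43% |
| 8 | 4% | 9% | 20% |

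With an unpaired t test the rate is at most 5.5% for shifts up to 5 mg/dL.

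**4. What the finger sticks can deliver.** At most 11 × 3 × 30 = 990 pairs per device; at the 80% compliance limit of the per-protocol set, 0.8 × 990 = 792. With relative-error SD 12% and 90 pairs per patient, the SE for one device is 12% × √([1 + 89·ICC]/990). The half-width of the 95% interval for the between-device difference is 1.96 × √2 × SE, treating the devices as independent:
- ICC 0: 1.1 percentage points
- ICC 0.05: design effect 5.45, SE 0.89%, half-width 2.5 points
- ICC 0.20: design effect 18.8, SE 1.65%, half-width 4.6 points

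At 100 mg/dL, 2.5 to 4.6 points is 2.5 to 4.6 mg/dL, about the size of the shifts in step 1. Below 70 there is much less information: at 6.7%, about 66 of 990 pairs.

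**The case against.** **MARD is not all the plan names.** A reader might infer that accuracy will be judged by MARD alone. The documents do not support that: they also name *accuracy* and *reliability*, nothing excludes signed bias, and the paired data are collected. This stands. The gap is that neither term is defined and no directional measure is specified.

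**No calibration difference is shown.** A reader might infer that a device artefact will be reported as an alarm effect. The documents do not support that either. Both devices come from one manufacturer, and the Study Background does not list accuracy among the differences between real-time systems. This stands, so the risk is conditional. But equal accuracy is nowhere stated, and the secondary objective treats it as open.

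**The artefact may not reach significance.** With the group t test named under General Principles, it would rarely do so for shifts up to 5 mg/dL. That is true of the p value, but the estimate would still carry the shift, and the same section also plans mixed-effects models for repeated measures.

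**A comparison of systems remains interpretable.** The protocol title speaks of systems. This stands, and it limits any remedy: alarm silencing, additional alerts and sensor duration, which the Study Background lists as differing between systems, may also differ here, so bias correction cannot isolate alarm type.

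**Finger sticks are not a neutral outcome.** A reader might want to use the proportion of capillary values below 70 as a device-independent check. The documents give no testing times and monitoring is unblinded, so patients may test when an alarm sounds. Nor would agreement in direction with a bias-adjusted analysis settle attribution, since both use the same capillary data and share the same period effects.

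**Conclusion.** The point holds as a conditional one. The documents establish that each device measures its own primary outcome, that alarm type is fully aliased with device, and that the only named accuracy metric cannot show the direction of error. They do not establish that the devices differ in calibration.

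If they did, a shift of 3 to 5 mg/dL would move measured time below 70 from 6.7% to 8.9–10.6% under the assumed mean 100 and SD 20 mg/dL. Whether that would be significant depends on period-to-period variability and the test used: 9% to 99% of paired analyses over the assumed range, at most 5.5% of unpaired ones.

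This is more than a missing detail, because MARD as written could not reveal the artefact. It is still a cheap improvement to the analysis and wording, not a fault in the data collection.

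**What to change.** Use the finger sticks already recorded, and settle the following before analysis:

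1. **Define accuracy** to include the mean signed difference (CGM minus capillary) for each device and the difference between devices, with confidence intervals clustered by patient, next to MARD. Give it overall and, descriptively only, in the low range.
2. **Add a bias-adjusted sensitivity analysis** of the primary comparison: correct each device's readings by its estimated mean signed difference and recompute the outcomes, carrying through the uncertainty of the correction. State that its precision is limited (half-width about 2.5 to 4.6 percentage points at an assumed ICC of 0.05 to 0.20). State also that few pairs fall below 70, so a correction driven by higher values may not apply there.
3. **Describe the primary contrast as between device systems**, not as an effect of alarm type alone. This is needed whatever items 1 and 2 show.

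No further measurements are needed. The cost is a little extra analysis, finger-stick meter error and wider intervals in the sensitivity analysis, and a more modest conclusion.
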